8.3 Procedure for Reporting to ViiV

All SAEs associated with administration of the injection will be reported to ViiV global safety case management within one business day of the first awareness using the SAE Case Report Form. A copy of this form will be kept on site. Non-serious drug related AEs to the injection will be reported within 5 calendar days of first becoming aware of the vent, with the exception of certain non-serious localized ISRs (listed above) which are not subject to these reporting requirements. In addition, notification about all SAE's considered related to VOCABRIA or to EDURANT identified during the course of the study will be notified to ViiV within 1 business day of the Sponsor's awareness.

The Individual Case Safty Reports will be sent to ViiV as follows:

Email for Clinical Safety Mailbox: [contact]

[contact]

Medical Device Incidents: Cabenuva is provided with vial adapters, needles and syringes for administration and is considered a combination product with a device component that is subject to regulatory post marketing safety reporting requirements. For I-TRAINs, the Principal Investigator will be responsible for the detection and documentation of events meeting the definition of device incidents/deficiencies that occur during this study. Should any person—either a study participant, or an associated person (non-study participant, e.g., a caregiver), or member of site staff—experience a device deficiency/incident, then a device deficiency form will be completed and sent to the sponsor within 24 hours of site awareness by the Principal Investigator. A copy of the form which includes instructions for reporting study participant and non-study participant information will be kept on site and is appended to this protocol (Appendix I).

Pregnancy: Participants of child-bearing potential will be reminded to inform their HIV provider immediately if they suspect that they are pregnant. If a pregnancy is reported, staff administering the injection will withhold the injection and the study clinician will record pregnancy information on the appropriate form and submit it to ViiV within 24 hours of learning of the pregnancy. The study clinician make the assessment, as described in Section 7.11, Clinical Management, above and discuss with the participant whether or not to continue the injection after making a benefit risk assessment. The pregnancy will be followed to determine outcome (including premature termination) and status of mother and child(ren). Pregnancy complications and elective terminations for medical reasons will be reported as an AE or SAE. Abnormal pregnancy outcomes (e.g. spontaneous abortion, fetal death, stillbirth, congenital anomalies, ectopic pregnancy) will be considered SAEs and reported as such. Prior to continuation of the injection following pregnancy, the following will occur:

- The study clinician will confirm that the injection can be continued, will document this, and this documentation will be stored within the participant file documents.

Protocol Title: **CAB-RPV LA Implementation Strategies for High-Risk Populations**

- The study clinician will reach out to ViiV and the BUMC IRB to obtain written approval. Staff administering the injection and the treating HIV clinician will monitor the outcome of the pregnancy and the status of the participant and their offspring.

Pregnancy Reporting to ViiV: Any pregnancy that occurs during study participation will be reported to ViiV Healthcare by the Sponsor within one week of first learning of its occurrence. The pregnancy should be followed up to determine its outcome and reported to ViiV Healthcare. SAEs occurring in association with a pregnancy after the participant has completed the study and considered by the HIV treating physician as possibly related to CABENUVA, will be reported to ViiV Healthcare/GSK within 1 business day of awareness.

It will be the responsibility of ViiV Healthcare/GSK's central safety department to forward information on pregnancies to the Antiretroviral Pregnancy Registry. The international registry is jointly sponsored by manufacturers or licensees of antiretroviral products. Additional information and a list of participating manufacturers/licensees are available from <http://apregistry.com/index.htm>.

Blank printed copies of all ViiV required documentation including the AE/ADR Intensity Form, Associated Person and Safety Reporting Information and Authorization Letter, IDSL Pregnancy and Pregnancy Notification Form, and Medical Combined Device Deficiency Form will be kept in folders at the study site. Copies of all required documentation will also be kept on the internal secure project drive.

9.0 Safety Review

This study is not intended to assess the efficacy of CAB-RPV LA as a medication; rather it is an implementation study to examine changing the service site of care delivery. CAB RPV-LA is already an approved medication that can be delivered to PLWH who receive care at CID. Thus, a DSMB is not required. However, in order to monitor safety of study participants in the pilot implementation trial, we will do the following: Any issues with the injections themselves will be recorded in logbooks. Special attention will be given to any medical issues related to the injections, including perceived soreness, fatigue, and other unintended consequences throughout the trial and standard referral to BMC will be made in such cases. We will also report all medication errors identified to the sponsor as required by ViiV. During analysis, we will categorize the errors into the four groups identified by ViiV in order to capture severity: medication errors associated with adverse events, medication errors without harm, intercepted (near miss) medication errors, and potential medication errors. VH has requested that all implementation studies involving the use of medications collect and report the following potential medical errors associated with administration of a medication: 1) Dosing errors, including incorrect loading dose, multiple loading doses, errors in maintenance dose (e.g. 3ml given instead of 2ml by accident), excess dose (e.g. two injections of one medication instead of one injection of each); 2) Faulty technique, including accidental IV or SC leading to partial IV administration, needle breakage, use of wrong needle, failure to fill syringe with medicine appropriately, multiple injections /re-injection on the same site (minimum gap), leakage from vial or syringe, leakage from injection site, healthcare provider needlestick injuries; 3) Other medication errors including delivery at a site other than the gluteal region, one injection of each drug but not on the same visit, storage at the wrong temperature, time outside refrigeration, use of expired medicine. These events will be reported through the Non-Serious Adverse Events/Adverse Drug Reaction Pages, Associated Person Safety Reporting Information and Authorization Letter, Medical Device or Combination Product with Device Deficiency/Incident Report Form, all attached in the Appendix of this document

Protocol Title: **CAB-RPV LA Implementation Strategies for High-Risk Populations**

We will also meet ViiV's expectations, including submission of all safety reports to all concerned parties, as well as reporting to concerned regulatory authorities. Medical governance for the study (i.e., welfare of the study population), in accordance with ICH Good Clinical Practice (GCP) all local regulations and legal requirements applicable to the study will be followed. Although this is an implementation study and safety incidents are unlikely, we will also report to ViiV the following safety information within their pre-specified timeframes: 1) serious adverse events (SAEs) and pregnancy reports for subjects exposed to VH medications during the course of the study using the VH SAE and/or pregnancy case report form pages; 2) any other significant safety issues relating to the VH study medication. Medical events related to underlying HIV disease will also be collected, reviewed by the infectious disease study clinician on our study team, and followed throughout the trial. This clinician will also review or provide consultation for each SAE as needed. These reviews will include an assessment of the possible relatedness of the event to the study procedures. The study clinician will also provide advice for decisions to exclude, refer, or withdraw participants as required. In the case of SAEs or AEs, the study clinician will complete the SAE/AE Drug Reaction pages and fax them to ViiV within 5 days for an adverse event, and within 24 hours/1 business day for serious adverse events per ViiV requirements. This document is attached to the IRB submission and is titled, "AE ADR Intensity GSK."

10.0 Data Handling and Record Keeping

10.1 Confidentiality

At the screening consent appointment, participants will complete the HIPAA Authorization to grant permission to study staff to review their EHR. After an individual provides informed consent for screening and HIPAA authorization, a clinician will review their most recent labs for genotype and viral load, which would typically be part of standard care, to determine if they are eligible for CAB-RPV LA. Results of this review will be used to determine final eligibility. Following this, the EHR will be reviewed at 3 months and 6 months to document information needed to evaluate outcomes using the Chart Review Form. Other clinical and demographic information will also be abstracted to enable investigators to better characterize the study sample and to use as covariates in analyses. There will be no additional clinical records kept specifically for the study. As CAB-RPV LA is one standard of care for HIV, record of injections received will also be recorded in the EHR. All study data will be stored on a secure, password protected computer. Additionally, although no personal or identifiable data will be collected beyond the informed consent form, all documents created, such as those related to analyses and findings, will be maintained in a locked filing cabinet and in a password-protected database only accessible to the researchers.

10.2 Study Records Retention

All data will be stored and maintained in line with current ethical standards. Personal and identifiable data will need to be collected for this study, including a locator form and other clinical data. Survey data on paper forms will be maintained in a locked filing cabinet and will not be linked to the informed consent document, which will be kept in a separate file. Each participant will be given a study identifier; the only document that will link individual names to this identifier will be a list maintained in a locked filing cabinet. A separate list will link the MRN to the identifier. Medical record numbers will not be included on any study data collection forms; only the study identifier will be used on data collection instruments. All documents created will be maintained in a locked filing cabinet and in a password-protected database only accessible to the researchers. All data will be maintained for seven years after the study is completed and then destroyed. The informed consent documents will also be destroyed at this time.

11.0 Statistical Plan

11.1 Study Hypotheses

Objective 2 has the following hypotheses:

- **H1:** Changing the service site will result in $\geq 80\%$ of participants in the community-based intervention arm beginning injections
- **H2:** Of participants in the community-based intervention arm who begin injections, 80% will complete 6 injections
- **H3:** Changing the service site will result in improved engagement in care for participants in the community-based intervention arm compared to matched controls (Cohort 3) at 6 months for intervention patients compared to control group patients
- **H4:** Changing the service site will result in superior HIV viral suppression at 6 months compared to for participants in the community-based intervention arm compared to matched controls (Cohort 3)
- **H5:** Participants in the community-based intervention arm will be equally satisfied with their care compared to patients who receive care in clinic settings (Cohort 2).

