1.2 Rationale & Purpose

Our proposed implementation research is designed to evaluate a novel approach to engage individuals with HIV who are at the highest risk for not accessing care or adhering to treatment. We are not testing CAB-RPV LA; this is an approved drug. We are also not studying the drug nor are we studying it for a new population, new dosage or new route of administration. Rather, we are conducting an implementation study and propose to test implementation CAB-RPV LA in community-based settings.

Strategies to implement evidence-based interventions to end the HIV epidemic are urgently needed. Despite highly effective antiretroviral treatment (ART) for HIV infection and multiple effective prevention interventions, there are approximately 40,000 new HIV infections annually in the US (CDC, 2019). Two of the four pillars of the US Department of Health and Human Services "Ending the HIV Epidemic" initiative are to:

Protocol Title: **CAB-RPV LA Implementation Strategies for High-Risk Populations**

1) treat individuals with HIV rapidly and effectively to achieve viral suppression; and 2) prevent new infections by using evidence-based interventions (<https://www.cdc.gov/endHIV/>).

Our implementation research addresses three ViiV Healthcare priority areas: 1) implementation of CAB-RPV LA delivery models in non-HIV clinic settings; 2) feasibility and acceptability of bringing CAB-RPV LA injections to the patient (rather than bringing the patient to the medication in more traditional ways only); and 3) addressing challenges of CAB-RPV LA delivery amongst high risk populations, specifically women and men of color, immigrants, homeless individuals, active substance users, transactional sex workers, individuals released from incarceration, and individuals who have fallen out of HIV care. Our study (which overall incorporates three Objectives) addresses the following research questions:

A. Implementation Questions

1. Will community-based delivery of CAB-RPV LA be an acceptable and feasible delivery method to high-risk PLWH from the patient, provider and community organization perspectives? (acceptability/feasibility)
2. Can a community-based delivery strategy lead to initiation and completion of injections for six months for at least 80% of individuals who are enrolled into Cohort 1 for an initial visit in an outreach setting? (reach)

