6.0 Study Intervention

The study intervention for Cohort 1 is delivery of HIV medication at Project Trust, rather than in the BMC HIV Clinic. Project Trust (PT) is a street-based drop-in clinic that is focused on STD testing, treatment, harm reduction, and social services engagement. PT engages in outreach work, provides individuals with substance use disorder safe injection kits, and is a well-established community site for the target population frequenting the area, which is home to a high number of individuals who are homeless, diagnosed with substance use disorder, and are living with HIV. Study staff who will be administering the injection are all trained clinicians (either nurse practitioners or physicians) and are BMC staff. Individuals administering the injection will all be listed on the BUMC Internal Review Board study protocol.

There is not a clinical intervention or any intervention beyond data collection for Cohorts 2 or Cohort 3. Cohort 2 will be receiving their CAB-RPV LA within the BMC HIV clinic as their standard care. Cohort 3 will be receiving standard of care (not CAB-RPV LA) and will be patients of the BMC HIV clinic. Individuals enrolled in all three cohorts will be asked to complete a survey at study enrollment (baseline), between 2-4 months after their enrollment (midpoint) and a final follow up between 6 - 8 months post baseline. Clinical data will be obtained from the BMC EHR via the clinical data warehouse at these time periods and no other data will be collected directly from study participants for Objective 2.

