If the participant chose's to not take the oral lead-in mediation, the participant will proceed directly to the initiation injection once they have completed all required lab work, including HIV labs confirming that they are virally suppressed (> 50 copies per mL), and a comprehensive metabolic panel. The participant and their clinician will determine a date for the initiation injection. As the medication will need to be obtained from the pharmacy, participants will not be able to receive their initiation injection on the same day as they are enrolled into the study.

- At the time of the injection, during the 15 minute waiting period, study staff will sit with the participant and remind them of the target date for the next injection. This date will be recorded in the study Log Book. The month following the initiation dose, participants receive a maintenance dose. Once the participant has received the maintenance dose, the participant and their clinician may discuss whether the participant would like to shift to receiving the injection every other month rather than every month. The clinician and the participant may choose whether to receive the injection every month, or every other month per CID standard of care and the medication package insert.
- One week prior to each scheduled injection date, study staff will contact participant via their preferred contact method determined on the Locator Form to confirm injection date and confirm with the community-based clinician administering the injection.
- One day prior to injection date, study staff will contact participant for reminder.

Below is a table that outlines when all evaluation activities occur:

Month	Cohort 1	Cohort 2	Cohort 3
1	
• Screening• Enrollment• Comprehensive Metabolic Panel• Baseline Data Collection• Participant may choose to take 28 days of Oral Lead-In medication• If participant opts out of the oral lead-in, they will receive their Initiation Injection during this time point	
• Screening• Enrollment• Baseline Data Collection	
• Screening• Enrollment• Baseline Data Collection
2	
• Oral lead-in: Initial Injection• No Oral Lead-In: Maintenance Dose		

Protocol Title: **CAB-RPV LA Implementation Strategies for High-Risk Populations**

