7.6 Injection Process and Safety Procedures

For patients enrolled in Cohort 1, injection procedures will be as follows:

- 15 minutes prior to the scheduled appointment time, the study clinician will remove the injection from refrigeration.
- Injections will be administered by a licensed healthcare professional (physician, nurse, nurse practitioner).
 - a. A complete dose will include two injections: one injection of cabotegravir and one injection of rilpivirine.
 - b. Each injection will be administered at separate gluteal injection sites during the same visit, with the ventrogluteal site recommended.
 - c. The clinician will consider the body mass index (BMI) of the patient to ensure that the needle length is sufficient to reach the gluteus muscle. Longer needle lengths (not included in the dosing kit) may be required for patients with higher BMI (greater than 30 kg/m²) to ensure that injections are administered intramuscularly as opposed to subcutaneously.
- The clinician and the participant will determine the target date for the next injection, which will occur between 25-32 days from initial injection. This discussion will happen while the participant waits for 15 minutes to ensure that no immediate adverse effects occur. This encounter and next planned injection date will be documented in the study Log Book by study staff. During this 15-minute period, the participant may also complete follow-up questionnaires if they are due for their three-month or six-month follow-up survey.
- Once the participant receives their second injection, they may discuss with their clinician whether they want to continue to receive their injection monthly, or whether they want to move to a bi-monthly schedule. The same procedures (confirming appointments in advance, removal from refrigerator, injection administration, monitoring period post-injection, scheduling of next injection, documentation in study log) will be used for follow-up injections
- Once the participant has been enrolled for at least 6 months in the study, they will be given the option to remain on CAB-RPV LA
 - a. That administration can take place either at PT or at CID depending on the participants preferences
 - b. If the participant wishes to receive their injection at CID, the study clinician will reach out to the participants CID provider so that the participant can begin to schedule their injections at CID

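### H2's fixed count of 6 injections scores a Cohort 1 participant who moves to every-other-month dosing at the earliest permitted point as a failure, even with full attendance

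*Combined protocol and SAP*

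**What the plan says.** Section 11.1 states H2 as "Of participants in the community-based intervention arm who begin injections, 80% will complete 6 injections". It gives no time horizon, no unit and no separate count for a less frequent schedule, and Sections 11.2 and 11.3 add none.

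The schedule itself is flexible. Section 7.1 says "The clinician and the participant may choose whether to receive the injection every month, or every other month", and Section 7.6 places the earliest decision point: "Once the participant receives their second injection, they may discuss with their clinician whether they want to continue to receive their injection monthly". The medication table in Section 7.0 and the evaluation table in Section 7.1 both carry separate monthly and bi-monthly entries for Cohort 1, with alternate months marked as having no injection on the bi-monthly schedule.

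Implementation Question 2 in Section 1.2 covers the same ground in different terms: "initiation and completion of injections for six months for at least 80% of individuals who are enrolled into Cohort 1". It refers to a period, not a count, and its denominator is those enrolled, whereas H2's is those who begin injections.

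**The concern.** H2 is the only one of the five hypotheses about completing injections. A fixed count of 6 matches a monthly schedule over six months, but the protocol offers a second schedule with fewer visits. A participant on that schedule who never misses a visit satisfies the six-month wording of Implementation Question 2 and yet counts against H2. Part of any shortfall from 80% could then reflect a permitted choice of schedule and be read as poor completion under community delivery, which is the implementation strategy being piloted.

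**Working it through.** **Inputs.** The months with an injection come from the tables in Sections 7.0 and 7.1, which agree and run to month 7. The cohort size of 20 is from Section 11.2. Endpoint data collection in the Section 7.1 table spans months 7 to 9. Visits in months 8 and 9, and all switches later than injection 2, are my extension of the same pattern (a two-month gap after the last monthly injection).

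**Step 1: reproduce the plan's figure.** Monthly with oral lead-in: months 2 to 7, which is 6 visits. Monthly without lead-in: months 1 to 6, also 6 visits (7 by month 7). The count of 6 therefore follows from six months of monthly dosing.

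**Step 2: count visits for each pathway.**

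| Lead-in | Switch after injection | Visit months | By month 6 | By month 7 | By month 9 |
|---|---|---|---|---|---|
| No | 2 (earliest) | 1, 2, 4, 6, 8 | 4 | 4 | 5 |
| No | 3 | 1, 2, 3, 5, 7, 9 | 4 | 5 | 6 |
| No | 4 | 1, 2, 3, 4, 6, 8 | 5 | 5 | 6 |
| No | 5 | 1–5, 7, 9 | 5 | 6 | 7 |
| No | none | 1–9 | 6 | 7 | 9 |
| Yes | 2 (earliest) | 2, 3, 5, 7, 9 | 3 | 4 | 5 |
| Yes | 3 | 2, 3, 4, 6, 8 | 4 | 4 | 5 |
| Yes | 4 | 2, 3, 4, 5, 7, 9 | 4 | 5 | 6 |
| Yes | 5 | 2–6, 8 | 5 | 5 | 6 |
| Yes | none | 2–9 | 5 | 6 | 8 |

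With the earliest switch, the sixth visit falls in month 10 (no lead-in) or month 11 (lead-in), after the evaluation table ends. Of the six later-switch patterns shown, one reaches 6 by month 7 and five do by month 9.

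**Step 3: effect on H2.** Assume 6 means visits, every starter attends every visit, switchers switch after injection 2, and the cutoff is month 7 or month 9. Then the highest attainable H2 proportion = (starters − early switchers) / starters.

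- 20 starters: 2 switchers, 18/20 = 90%; 4, 16/20 = 80%; 5, 15/20 = 75%; 10, 10/20 = 50%.
- 16 starters (H1's minimum, 0.80 × 20): 3 switchers, 13/16 = 81%; 4, 12/16 = 75%; 8, 8/16 = 50%.

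At a month-6 cutoff these are only upper bounds, because a monthly participant with lead-in has 5 visits by then and also fails.

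**Step 4: the unit.** Section 7.6 also says "A complete dose will include two injections: one injection of cabotegravir and one injection of rilpivirine". Counted singly, 6 injections would be 6/2 = 3 visits, reached in month 3 or 4 if monthly and month 4 or 5 with the earliest switch (without or with lead-in). That would not measure six months of completion. Section 7.6's own reference to a second injection, and both tables, count visits, so 6 visits is the natural reading.

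**Step 5: number due in six monthly slots from the first injection.** No switch: 6. Switch after injection 2 or 3: 4. Switch after injection 4 or 5: 5. These hold with or without lead-in.

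**The case against.** The strongest case against is one of weight. H2 is unpowered (Section 11.2 powers the study on H4), has no test or decision rule, and belongs to a pilot with 20 per cohort. The share and timing of switching are assumed throughout, and with 20 starters early switching alone forces a miss of 80% only if 5 or more switch. Injections are recorded in the EHR (Section 10.1), so a count by schedule could be made at analysis anyway. All of this stands. It limits the consequences but does not remove the mismatch, and a completion rule chosen after the data are seen is weaker than one fixed beforehand.

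The events/trials model in Section 11.3 could accommodate different numbers of visits per person, but it is specified for engagement in care, does not name injection visits and does not define H2 completion.

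A reader might infer that 6 can be reached only by staying monthly. The tables do not support that: without lead-in, a switch after injection 5 still gives 6 visits by month 7, and by month 9 most later switchers have 6 or more. A reader might also apply the ceilings in the working at month 6. They are not exact there, and the Section 7.1 table does not begin endpoint collection until month 7.

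**Conclusion.** The concern holds for participants who switch at the earliest permitted point. They have 4 visits due by month 7 and 5 by month 9, and H2 scores full attendance as failure. By month 7 it also catches most, but not all, later switchers. For participants who stay monthly, 6 visits by month 7 is a fair measure of completion.

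The size depends on a switching share that the documents do not give. Under the assumptions in the working, each early switcher among 20 starters lowers H2's ceiling by 5 percentage points, and the fifth takes it below target. With no switchers the ceiling at month 7 is 100%. It would go too far to say that H2 is bound to fail or that the sample size is wrong; neither follows. H2 should be reworded before analysis.

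**What to change.** Change Section 11 only.

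- Restate H2: at least 80% of starters receive all dosing visits due over six monthly slots from the first injection (months 1–6 without lead-in, 2–7 with).
- Set the number due by the frequency, monthly or every other month, logged before each slot: 6 if monthly throughout, 4 after a switch at injection 2 or 3, 5 after a switch at injection 4 or 5. A missed monthly visit then cannot be relabelled afterwards.
- State that a late or missed visit that resets the next planned date (Section 7.7) does not reduce the number due. State also how a postponement directed by Section 7.8 after a dosing error is counted.
- State that the unit is a dosing visit, that starters who stop or are lost count as not complete, and that the denominator is those who begin injections, noting that Implementation Question 2 uses those enrolled.
- Report the proportion overall and by schedule.

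The cost is revised wording in Section 11.1 and a line in Section 11.3. Injections are already in the EHR, and Section 7.6 provides that "This encounter and next planned injection date will be documented in the study Log Book by study staff". The endpoint chart review must fall after the sixth slot, which is month 7 for lead-in participants; Section 6.0's "a final follow up between 6 - 8 months post baseline" allows that.

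The definition becomes slightly more complex, and completion is easier with fewer visits due. For illustration, at an assumed 95% independent attendance at each visit after the first, full completion is 0.95^5 = 77% with 6 due and 0.95^3 = 86% with 4 due; at 90% it is 59% and 73%. The by-schedule table makes this visible. No dose, injection schedule or clinical rule changes.
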